6.5.5. Correlation between DEXA and BIA

For lean body mass (%) and body fat (%), scatter plots of observed values measured by DEXA and BIA at the same visit will be presented. All cohorts and visits will be plotted in the same figure in different symbols. The correlation coefficient will be calculated.

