
 To evaluate the effects of somatropin on other body composition parameters. 	
 Population: Japanese participants with PWS syndrome in each cohort; Variable: Each secondary endpoint; Intercurrent events: All data after an intercurrent event (major deviation of diet/exercise, discontinuation of treatment, discontinuation of study, etc.), if collected, will not be considered; Population level summary: Mean (GH naïve pediatric and GH treated pediatric cohort) or mean/LS mean (adult cohort). 	
 [KEY SECONDARY] Change from baseline to Month 12 in lean body mass (%) measured by BIA; Change from baseline to Month 12 in body fat (%) measured by DEXA; Change from baseline to Month 12 in adipose tissue distribution measured by abdominal CT; Change from baseline to Month 6 in lean body mass (%) measured by DEXA (adult cohort only).

 To evaluate the safety and tolerability of somatropin. 	
 N/A. 	
 AE. SAE. Clinical laboratory values. Bone maturation.
CCI		

CCI		
[REDACTED]	[REDACTED]	[REDACTED]
[REDACTED]	[REDACTED]	[REDACTED]
[REDACTED]	[REDACTED]	[REDACTED]

Overall Design

Brief Summary

This is a multicenter, open label, multi cohort study of participants with PWS. This study has 3 cohorts (GH naïve pediatric cohort, GH treated pediatric cohort and adult cohort) and all participants will receive somatropin.

Number of Participants

Approximately 30 Japanese participants (5 GH naïve pediatric participants, 5 GH treated pediatric participants and 20 adult participants) will be enrolled to study intervention.

Intervention Groups and Duration

The study consists of a screening period, treatment period of 12 months and extension period which continues for 36 months or until regulatory approval, whichever occurs first. Upon commencement of active treatment with somatropin, participants will be dosed 6 or 7 times in a week, subcutaneously.

Dose regimens in each of the cohorts are as below (the weekly dose should be divided into 6 or 7 subcutaneous injections):

- GH naïve pediatric cohort: 0.245 mg/kg/week;
- GH treated pediatric cohort: 0.084 mg/kg/week. The dosage may be adjusted according to participants' symptoms and serum IGF-1 levels but should not exceed 1.6 mg/day;

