Blood count	X	X			X	X		X	X	X		
Blood chemistry	X	X			X	X		X	X	X		
IGF-1, IGF-1 SDS	X	X	X		X	X		X	X	X		
Thyroid function (TSH, FT4)	X	X	X		X	X		X	X	X		
Cortisol	X	X	X		X	X		X	X	X		
Gonadal function (LH, FSH, E2, testosterone)	X	X				X		X	X	X		
HbA1c	X	X	X	X ^b	X	X	X	X	X	X	X	
Casual blood glucose		X ^b	X ^b	X ^b	X ^b	X ^b	X ^b	X ^b	X ^b	X ^b	X ^b	
Lipid profile	X	X			X	X		X	X	X	X	

PFIZER CONFIDENTIAL

	Screening Period	Treatment Period								Extension Period ^l	End of Study	Follow-up
		Day 1 ^h	Month 1 Week 4	Month 2 ^b Week 8	Month 3 Week 12	Month 6 Week 26	Month 9 Week 39	Month 12 Week 52	Month 18/24/30/36/42 Week 78/104/130/156/182			
Visit Identifier^a Abbreviations used in this table may be found in Appendix 11	Screening									End of Study/Early Termination/Discontinuation	28 days after EOS visit ^k	
Visit Window	Day -28 to -1	N/A	±3d	±3d	±3d	±3d	±7d	±7d	±14d			+7d

a. Day relative to start of study intervention (Day 1).
b. Applicable only for participants with diabetes.
c. For pediatric cohorts only. If the participant reaches bone age of 17 for boys and 15 for girls, the assessment is not necessary after that.
d. Applicable only for early termination before Month 12.
e. For adult cohort only.
f. For extension period, study intervention can be dispensed every 3 months in case a participant cannot bring home a 6-month drug supply at once. If a participant chooses to receive drug supply every 3 months, safety assessment (at least but not limited to: AE/SAE, concomitant treatment) should be confirmed via physical site visit or telehealth before dispensing for the remaining 3 months. If a participant choose a 6-month drug supply, he/she will come back to the site for next protocol specified visits and complete assessments according to protocol.
g. All laboratory testing can be performed locally at the site. Fasting is not required for any of lab tests in this study.
h. Laboratory test result at Screening can be used for Day 1 if the test was performed within 7 days before Day 1 visit.
i. Height measurement at Screening can be used for Day 1 if the measurement was performed within 14 days before Day 1 visit.
j. DEXA/Abdominal CT scan prior to Day 1 visit is acceptable if the evaluation was performed within 7 days before Day 1 visit.
k. Follow-up visit may become telephone visit at investigator's discretion.

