3.2. Secondary Endpoint(s)

The secondary endpoints for the study are as follows.

- [KEY SECONDARY] Change from baseline to Month 12 in lean body mass (%) measured by BIA.
- Change from baseline to Month 12 in body fat (%) measured by DEXA.
- Change from baseline to Month 12 in adipose tissue distribution measured by abdominal CT.
- Change from baseline to Month 6 in lean body mass (%) measured by DEXA (adult cohort only).

CCI

IGF-1 SDS will be determined from the age and gender standards listed in the article by Isojima T. *et al.*¹.

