6. ANALYSES AND SUMMARIES

Unless otherwise specified, data will be summarized by each cohort.

For change from baseline endpoints, it would require that a participant have a baseline value and at least 1 post baseline value to be included in the analysis for that endpoint.

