6.1.1.1. Main Analysis

- Estimand strategy: Hypothetical (section 2.1.1).
- Analysis set: Efficacy Evaluable Set (Adherence to protocol regimen) (section 4).
- Analysis methodology: In adult cohort, change from baseline will be analyzed using a MMRM including data from Month 6, and 12 with visit, baseline value, and baseline value-by-visit interaction as fixed effects. In GH naïve pediatric and GH treated pediatric cohort, observed value and change from baseline will be summarized descriptively (section 5.2.2).

- Intercurrent events and missing data: All data after an intercurrent event (major deviation of diet/exercise, discontinuation of treatment, discontinuation of study, etc.), if collected, will not be considered. No imputation will be made for missing data.
- In adult cohort, the LS mean and its 95% CI will be presented. In GH naïve pediatric and GH treated pediatric cohort, the descriptive summary statistics will be presented.

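### SAP 6.5.5 compares BIA with DEXA only by correlating levels, which hardly shows whether BIA follows change, the quantity of the key secondary endpoint

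*SAP*

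**What the plan says.** SAP 6.5.5 covers lean body mass (%) and body fat (%). It states that "scatter plots of observed values measured by DEXA and BIA at the same visit will be presented", then "All cohorts and visits will be plotted in the same figure in different symbols", and ends with "The correlation coefficient will be calculated". It does not give the type of coefficient, the grouping, a confidence interval or any treatment of repeated visits. The opening of SAP section 6 sets a default: "Unless otherwise specified, data will be summarized by each cohort".

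Change from baseline to Month 12 in lean body mass (%) by BIA is labelled the key secondary endpoint (SAP 3.2). Adult DEXA change and adult BIA change are each analysed in their own MMRM (SAP 6.1.1.1 and 6.2.1.1). The pediatric changes are summarised descriptively. SAP 5.1 rules out formal hypothesis testing and says efficacy will be judged from individual data and summary statistics, together with a check that the adult LS mean of the DEXA primary endpoint is above 0.

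**The concern.** The BIA endpoint is a change within a person, but 6.5.5 correlates levels across people. People differ widely in body composition, so two methods that rank them similarly will correlate well even if one of them does not register treatment change. Correlation is also not agreement, because a BIA that reads a fixed amount too high or too low gives the same r.

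There is no formal test, and efficacy rests on an overall reading of the summaries. A high coefficient could therefore be taken as evidence that BIA corroborates the DEXA change, which it cannot show.

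**Working it through.** The plan gives no correlation, standard deviation or error figure, so there is nothing to reproduce. The variances below are assumptions.

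**Data layout.** The Protocol synopsis plans "5 GH naïve pediatric participants, 5 GH treated pediatric participants and 20 adult participants". Adults have DEXA at baseline, Month 6 and Month 12. In the Schedule of Activities the Month 6 scan carries the footnote "For adult cohort only", so children have two scans. With complete data there are 20 × 3 + 10 × 2 = 80 pairs from 30 people.

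**Constant offset.** If BIA reads b points too high throughout, then cov(D, B + b) = cov(D, B) and var(B + b) = var(B). The coefficient is unchanged for any b.

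**Body fat adds nothing.** SAP section 3 uses the same denominator, lean plus fat, for both percentages, so fat % = 1 − lean %. Since corr(1 − x, 1 − y) = corr(x, y), the body-fat coefficient equals the lean-mass one.

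**Worked case, adults (percentage points).** Assumed SDs are: between people 6, true change 2 (independent of baseline), DEXA error 1, BIA visit error 2, BIA person offset 2.5. The assumed mean change is 3.

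*Correlation of levels at Month 12:*
- BIA tracks none of the change: cov = 36; var(DEXA) = 36 + 4 + 1 = 41; var(BIA) = 36 + 6.25 + 4 = 46.25; r = 36/√(41 × 46.25) = 0.83.
- BIA tracks all of it: cov = 36 + 4 = 40; var(BIA) = 46.25 + 4 = 50.25; r = 40/√(41 × 50.25) = 0.88.

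At baseline both cases give 36/√(37 × 46.25) = 0.87.

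*Correlation of changes from baseline to Month 12:*
- None: cov = 0, so r = 0.
- All: cov = 4; var(DEXA change) = 4 + 2 × 1 = 6; var(BIA change) = 4 + 2 × 4 = 12; r = 4/√72 = 0.47. With BIA visit error SD 1 it is 4/√(6 × 6) = 0.67; with SD 3 it is 4/√(6 × 22) = 0.35.

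*Mean difference of changes (BIA minus DEXA), n = 20, t = 2.09:*
- None: mean −3; SD = √(4 + 2 + 8) = 3.74; 95% CI half-width 2.09 × 3.74/√20 = 1.75; limits of agreement −3 ± 1.96 × 3.74, or −10.3 to 4.3.
- All: mean 0; SD = √(2 + 8) = 3.16; half-width 1.48; limits ±6.2.

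**Pooled coefficient, by simulation of the 80 pairs.** With mean changes of 5, 0 and 3 points (GH naïve, GH treated, adult) and cohort means 7 points apart, pooled r averages 0.88 with no tracking (5–95% range 0.82–0.93) and 0.92 with full tracking (0.88–0.95). The ranges overlap.

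| Assumptions varied | Statistic | No tracking | Full tracking |
|---|---|---|---|
| Between-person SD 4–8, with or without cohort differences | Pooled level r | 0.66–0.92 | 0.79–0.94 |
| Same | Adult-only level r | 0.67–0.89 | 0.78–0.92 |
| Same | Adult change r | about 0 | about 0.47 |
| Wider grid: SD 5–10, baseline DEXA–BIA r 0.80–0.98 | Pooled level r | 0.68–0.97 | up to 0.99 |
| Same grid | Change r, all cohorts together | about 0 | 0.37–0.95 |

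The upper end of the last row partly reflects different mean changes between cohorts, so it should not be read as an adult-only figure.

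**Precision of the change correlation (Fisher z, 95%).** At n = 20, r = 0.47 has an interval of about 0.04 to 0.76, and r = 0 has −0.44 to 0.44. At n = 5, r = 0.47 has about −0.70 to 0.96.

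**The case against.** The strongest reply is that a BIA blind to treatment would show up elsewhere. If DEXA gained 3 points and BIA gained none, the two adult LS means would differ visibly. That stands. A reader might call 6.5.5 the only check of BIA against DEXA, but the documents do not support that: both mean changes are estimated, and redacted sections may hold more. The separate summaries do not show whether the same participants change on both methods, or by how much the methods differ within a person.

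A reader might also infer that one coefficient pooled over cohorts and visits is specified. The pooling sentence governs the figure, the coefficient sentence is silent, and section 6 defaults to by cohort. Pooling is a natural reading but not a stated one. The by-cohort reading does not cure the problem, since adult-only level r behaves almost the same way.

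Nor can it be said that the coefficient will stay near 0.9. That depends on assumed spread and error, and 0.66 is equally compatible with no tracking. Repeated pairs per person matter little here because no interval or test is planned for the coefficient.

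Finally, the change correlation has limits of its own. It is imprecise at n = 20 and uninformative at n = 5. It would also be near 0 if everyone responded equally and BIA followed perfectly. This stands, and is why it should accompany the mean difference and limits of agreement and not replace them.

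**Conclusion.** The point holds as a modest improvement to a descriptive analysis. The planned statistic cannot show agreement and separates a BIA that follows change from one that does not only weakly: 0.83 against 0.88 for adult levels at Month 12 in the worked case, compared with 0 against 0.47 for changes and −3 against 0 points for the mean difference in change. All these sizes rest on assumed variances. The offset result and the duplication of the body-fat coefficient are algebraic and need no assumption.

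No decision rule uses the coefficient, BIA change is analysed directly, and the primary DEXA result is untouched. What is at stake is how far BIA can be said to support DEXA.

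**What to change.** Amend SAP 6.5.5 as follows.

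- **Adult cohort:** report the BIA-minus-DEXA mean difference with 95% limits of agreement for levels at baseline, Month 6 and Month 12, and for change from baseline to Months 6 and 12, using one pair per participant per visit. Add a change-on-change scatter plot and the correlation of changes with its confidence interval.
- **Pediatric cohorts (5 each):** show individual paired values and changes, without coefficients.
- **Existing pooled plot:** keep it as illustration. State the type and grouping of any level correlation that is retained.
- **Body fat (%):** drop the separate coefficient, or note that it repeats the lean-mass one.

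The cost is SAP wording and one extra table or figure from data already collected. The adult change correlation will be imprecise and should be presented as such.

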6.6. Safety Summaries and Analyses

All analyses will be performed for FAS.

6.6.1. Adverse Events

Incidence of TEAEs and SAEs will be summarized according to CaPS.

Incidence of all-causality and treatment-related TEAEs of special interest will be summarized by SOCs and PTs. AEs of special interest will be defined in the safety narrative plan.

6.6.2. Laboratory Data

Laboratory data will be summarized in accordance with CaPS.

6.6.3. Other Safety Endpoints

- Vital Signs

Vital sign data will be summarized in accordance with CaPS.

- Bone Age, Bone maturation

Bone age and bone maturation will be reported in a list. Bone maturation will be calculated as bone age / chronological age.

- Physical Examinations, including Behavioral and Mental Health Status

Physical Examinations will be reported in a list.

- Height, Height SDS, and Weight

Observed value and change from baseline will be summarized according to CaPS.

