1.3. Schedule of Activities

The SoA table provides an overview of the protocol visits and procedures. Refer to the **STUDY ASSESSMENTS AND PROCEDURES** section of the protocol for detailed information on each procedure and assessment required for compliance with the protocol.

The investigator may schedule visits (unplanned visits) in addition to those listed in the SoA table, in order to conduct evaluations or assessments required to protect the well-being of the participant.

	Screening Period	Treatment Period								Extension Period ^l	End of Study	Follow-up
Visit Identifier^a Abbreviations used in this table may be found in Appendix 11	Screening	Day 1 ^b	Month 1 Week 4	Month 2 ^b Week 8	Month 3 Week 12	Month 6 Week 26	Month 9 Week 39	Month 12 Week 52	Month 18/24/30/36/42 Week 78/104/130/156/182	End of Study/Early Termination/Discontinuation	28 days after EOS visit ^k	
Visit Window	Day -28 to -1	N/A	±3d	±3d	±3d	±3d	±7d	±7d	±14d			+7d
Informed consent/assent	X											
Registration	X											
Inclusion/exclusion criteria	X	X										
Medical history	X	X										
Demographics	X	X										
Physical examination, including behavioral and mental health status	X	X										
Vital signs	X	X	X	X ^b	X	X	X	X	X	X		
Diet/exercise management compliance check	X	X	X		X	X	X	X	X			
Weight, BMI	X	X	X		X	X	X	X	X ^m	X		
Height ⁱ	X	X ^c	X ^c		X ^c	X ^c	X ^c	X	X ^{c, m}	X		
Bone age ^c		X						X		X ^d		
Assessment of childbearing potential	X											
Pregnancy testing (WOCBP only)	X					X		X	X	X		

PFIZER CONFIDENTIAL

	Screening Period	Treatment Period								Extension Period ^l	End of Study	Follow-up
		Day 1 ^h	Month 1 Week 4	Month 2 ^b Week 8	Month 3 Week 12	Month 6 Week 26	Month 9 Week 39	Month 12 Week 52	Month 18/24/30/36/42 Week 78/104/130/156/182			
Visit Identifier^a Abbreviations used in this table may be found in Appendix 11	Screening											
Visit Window	Day -28 to -1	N/A	±3d	±3d	±3d	±3d	±7d	±7d	±14d			+7d
Contraception check (WOCBP only)		X	X		X	X	X	X	X	X	X	X
Study intervention												
Dispense study intervention		X	X		X	X	X	X	X ^f			
Review injection diary			X		X	X	X	X	X		X	
Assessments												
Efficacy												
Body composition (DEXA) ^j		X				X ^e		X		X ^d		
Abdominal CT ^j		X						X		X ^d		
Body composition (BIA)		X	X		X	X	X	X	X ^m	X		
Waist circumference		X						X		X ^d		
Safety												
Concomitant treatment(s)		X	→	→	→	→	→	→	→	→	X	
Serious and nonserious adverse event monitoring	X	→	→	→	→	→	→	→	→	→	X	
Laboratory ^g												

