9. STATISTICAL CONSIDERATIONS

Detailed methodology for summary and statistical analyses of the data collected in this study is outlined here and further detailed in a SAP, which will be maintained by the sponsor. The SAP may modify what is outlined in the protocol where appropriate; however, any major modifications of the primary endpoint definitions or their analyses will also be reflected in a protocol amendment.

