9.3.1. General Considerations

All efficacy analyses will be performed on the efficacy evaluable set and all safety analyses will be performed on the FAS. All listings will be generated on the FAS.

Descriptive statistics consists of measures such as N, counts and percentages for categorical variables and N, mean, SD, median, range, min, max for continuous variables.

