9.3.5. Other Safety Analyses

AEs and SAEs (including local tolerability), discontinuations, and changes in vital signs, bone maturation, and clinical laboratory parameters will be descriptively summarized, and will be presented in tabular and/or graphical format. No imputation will be made for missing safety data.

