2.1. Study Objectives, Endpoints, and Estimands

Objectives	Estimands	Endpoints
Primary:	Primary:	Primary:

 To evaluate the efficacy of somatropin in participants with PWS. 	
 Population: Japanese participants with PWS in each cohort; Variable: Change from baseline to Month 12 in lean body mass (%) measured by DEXA; Intercurrent events: All data after an intercurrent event (major deviation of diet/exercise, discontinuation of treatment, discontinuation of study, etc.), if collected, will not be considered; Population level summary: Mean [Growth Hormone (GH) naïve pediatric and GH treated pediatric cohort] or LS mean (adult cohort). 	
 Change from baseline to Month 12 in lean body mass (%) measured by DEXA.
Secondary:	Secondary:	Secondary:

 To evaluate the effects of somatropin on other body composition parameters. 	
 Population: Japanese participants with PWS in each cohort; Variable: Each secondary endpoint; Intercurrent events: All data after an intercurrent event (major deviation of diet/exercise, discontinuation of treatment, discontinuation of study, etc.), if collected, will not be considered; Population level summary: Mean (GH naïve pediatric and GH treated pediatric cohort) or mean/LS mean (adult cohort). 	
 [KEY SECONDARY] Change from baseline to Month 12 in lean body mass (%) measured by BIA; Change from baseline to Month 12 in body fat (%) measured by DEXA; Change from baseline to Month 12 in adipose tissue distribution measured by abdominal CT; Change from baseline to Month 6 in lean body mass (%) measured by DEXA (adult cohort only).

 To evaluate the safety and tolerability of somatropin. 	
 N/A. 	
 AE.

Objectives	Estimands	Endpoints
		
 • SAE. • Clinical laboratory values. • Bone maturation.
CCI		

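### Does listing bone maturation, instead of summarizing its change as the protocol describes, leave a gap in the safety analysis?

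*SAP*

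**What the plan says.** SAP 2.1 names "Bone maturation" among the endpoints for the safety and tolerability objective, as do the protocol's own objectives tables.

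Protocol 9.3.5 groups it with other safety measures: "changes in vital signs, bone maturation, and clinical laboratory parameters will be descriptively summarized, and will be presented in tabular and/or graphical format". Protocol 9.3.1 explains what descriptive statistics are for continuous data ("N, mean, SD, median, range, min, max for continuous variables") and mentions listings separately: "All listings will be generated on the FAS".

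SAP 6.6.3 is narrower: "Bone age and bone maturation will be reported in a list. Bone maturation will be calculated as bone age / chronological age". In that same section, height, height SDS and weight do get a summary of observed values and change, while physical examinations get a list. The SAP's general default is "Unless otherwise specified, data will be summarized by each cohort".

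On the relation between the two documents, Protocol section 9 states: "The SAP may modify what is outlined in the protocol where appropriate". It reserves protocol amendments for major changes to the primary endpoint definitions or their analyses. SAP section 2 says the same.

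**The concern.** On a plain reading, the protocol promises a summary of change and the SAP delivers a list of values. The documents treat these as different outputs, so a list cannot simply be called a summary. The SAP's by-cohort default does not close the gap either, because 6.6.3 specifies something else for this endpoint. Of the items named in Protocol 9.3.5, bone maturation is the only one for which the SAP plans no summary, and neither 6.6.3 nor the SAP version history says why.

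At stake is whether the treatment-period report would lack a cohort-level result, and a stated change from Day 1, for a named pediatric safety endpoint. Protocol 2.2.1 also reports from the earlier pediatric trials that treatment did not speed up bone age, so readers may look for the matching result here.

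**Working it through.** The mismatch is textual, and the plan states no figure to reproduce. The check has two parts: is the departure allowed, and would the missing table tell a reader anything the list does not?

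**1. Is it allowed?** Yes. Bone maturation is not the primary endpoint, so the SAP may change its handling without an amendment, and neither document requires such a change to be labelled. SAP 6.6.3 gives bone age its own bullet, next to a different rule for height and weight, which reads as a choice. The version history records differences between SAP versions, not departures from the protocol. If the list was already in version 1, whose entry is N/A, no later entry would be expected.

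**2. How much data is involved?**
- Planned pediatric participants: 5 GH naïve + 5 GH treated = 10 (Protocol 1.1).
- Bone age in the Schedule of Activities: Day 1, "Month 12 Week 52", and early termination before Month 12. None is scheduled at the extension visits.
- Footnote c, Protocol 8.2.1 and SAP 3.5.3 end the assessment once bone age reaches 17 in boys or 15 in girls. The GH treated cohort enrols participants about to complete treatment for short stature (Protocol 5.1, criterion 10) and has no stated upper age limit. Some may have no second film.

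Ten children with two films each is therefore a maximum.

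**3. What can a reader get from the list?** Let BA be bone age and CA chronological age. The list gives BA and BA/CA for each child. The change in each is a subtraction, and CA is BA divided by the ratio, up to rounding. SAP 6.6.3 does not fix the list's columns, so a change column is unspecified, not excluded.

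Showing both measures matters more than averaging one. Two illustrative children over one year (baselines are assumptions):
- CA 6, BA 4.2, pace 1.0: 4.2/6 = 0.700 to 5.2/7 = 0.743, change +0.043.
- CA 6, BA 6.0, pace 1.3: 6.0/6 = 1.000 to 7.3/7 = 1.043, change +0.043.

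The ratio change is the same, but bone age rises by 1.0 and 1.3 years. A cohort mean of change in the ratio alone would hide that difference. The list shows it.

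The raw gain is also nearly an annual rate. The Month 12 window is Day 364 ± 7, or Days 357 to 371. (357 − 1)/365.25 = 0.975 years and (371 − 1)/365.25 = 1.013 years. A gain of 1.0 is then a rate of 1.0/0.975 = 1.026 to 1.0/1.013 = 0.987, within 2.6%.

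**4. What would a cohort mean add?** Assume a reading SD s of 0.25 to 0.5 years per film (not in the documents) and n = 5.
- SD of one child's change = √2 × s = 0.354 to 0.707.
- SE of the mean = SD/√5 = 0.158 to 0.316.
- 95% half-width = 2.776 × SE = 0.44 to 0.88 years.

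The contrast between a pace of 1.0 and one of 1.3 is 0.3 years. For the half-width to reach 0.3, s would have to be 0.3 × √5/(2.776 × √2) = 0.17 years or less, before counting any true variation between children. Fewer paired films would widen the interval further.

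**The case for a change.** The best case for a change is consistency. The protocol made a specific promise about a named endpoint and the SAP does not keep it. Small numbers cannot be the SAP's unstated reason, because the same two cohorts of about 5 get descriptive statistics for the primary endpoint (SAP 6.1.1.1) and for the other Month 12 body composition endpoints. The films are already scheduled, so the remedy is one small table or one sentence of explanation. A permission to modify is also not a statement that this particular modification was meant.

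Much of this stands. The texts do differ, no reason is given, and the remedy would be cheap. What does not follow is that the report would lose information. Change is not ruled out of the list, every child's values appear in it, and with at most 5 paired values per cohort those individual values are the main evidence whether or not a mean is printed beside them. A table added only to match the protocol's wording would be tidy, but it would not inform anyone further.

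**Conclusion.** The discrepancy is real but needs no change. The SAP is entitled to replace the protocol's summary with a list for a safety endpoint, and it does so in explicit terms. The list covers at most about 10 children and shows each one's bone age and ratio, from which every change can be derived. No efficacy result depends on it, and a cohort summary would not alter the safety reading.

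The permission and the maximum of 10 children come directly from the documents. That a cohort mean adds little rests on the assumed reading SD of 0.25 to 0.5 years. The conclusion on precision would weaken only if reading SD were about 0.17 years or less and children in a cohort hardly differed in pace. Even then the list would carry the same data.
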